The adverse event severity grading scale for the NCI CTCAE version 5.0 will be used for assessing adverse event severity. Below Table should be used for assessing severity for adverse events that are not specifically listed in the NCI CTCAE.

Adverse Event Severity Grading Scale for Events Not Specifically Listed in NCI CTCAE
Grade Severity

Grade	Severity
1	Mild; asymptomatic or mild symptoms; clinical or diagnostic observations only; or intervention not indicated
2	Moderate; minimal, local, or non-invasive intervention indicated; or limiting age-appropriate instrumental activities of daily living ^a
3	Severe or medically significant, but not immediately life-threatening; hospitalization or prolongation of hospitalization indicated; disabling; or limiting selfcare activities of daily living ^{b,c}
4	Life-threatening consequences or urgent intervention indicated ^d
5	Death related to adverse event ^d

NCI CTCAE = National Cancer Institute Common Terminology Criteria for Adverse Events.

Note: Based on the most recent version of NCI CTCAE version 5.0, which can be found at: http://ctep.cancer.gov/protocolDevelopment/electronic_applications/ctc.htm

a. Instrumental activities of daily living refer to preparing meals, shopping for groceries or clothes, using the telephone, managing money, etc.

b. Examples of self-care activities of daily living include bathing, dressing and undressing, feeding oneself, using the toilet, and taking medications, as performed by patients who are not bedridden.

c. If an event is assessed as a "significant medical event," it must be reported as a serious adverse event

d. Grade 4 and 5 events must be reported as serious adverse events

F. Pregnancy

If a female subject becomes pregnant while receiving the study drug or within 24 weeks after the last dose of study drug, a report should be completed and expeditiously submitted to Genentech, Inc. Pregnancies will be followed up until the outcome of the pregnancy is known, whenever possible, based upon due diligence taken to obtain the follow-up information. Abortion, whether accidental, therapeutic, or spontaneous, should always be classified as serious, and expeditiously reported as an SAE. Similarly, any congenital anomaly/birth defect in a child born to a female subject exposed to the study drug should be reported as an SAE.

G. AEs of Special Interest (AESIs)

AESIs are a subset of Events to Monitor (EtMs) of scientific and medical concern specific to the product, for which ongoing monitoring and rapid communication by the Investigator to the Sponsor is required. Such an event might require further investigation in order to characterize and understand it. Depending on the nature of the event, rapid communication by the trial Sponsor to other parties (e.g., Regulatory Authorities) may also be warranted.

Adverse events of special interest for this study include the following:

- Cases of potential drug-induced liver injury that include an elevated ALT or AST in combination with either an elevated bilirubin or clinical jaundice, as defined by Hy's law:
 - Treatment-emergent ALT or AST > 3 x ULN in combination with total bilirubin > 2 x ULN
 - Treatment-emergent ALT or AST > 3 x ULN in combination with clinical jaundice
- Data related to a suspected transmission of an infectious agent by the study drug (STIAMP), as defined below:
 - Any organism, virus, or infectious particle (e.g., prion protein transmitting transmissible spongiform encephalopathy), pathogenic or non-pathogenic, is considered an infectious agent. A transmission of an infectious agent may be suspected from clinical symptoms or laboratory findings that indicate an infection in a patient exposed to a medicinal product. This term applies only when a contamination of the study drug is suspected

Ocrevus does not have product specific Adverse Events of Special Interest.

H. Other Special Situations Reports

The following other Special Situations Reports should be collected even in the absence of an Adverse Event and transmitted to Genentech:

- Data related to the Product usage during breastfeeding
- Data related to overdose, abuse, misuse or medication error (including potentially exposed or intercepted medication errors)
- In addition, reasonable attempts should be made to obtain and submit the age or age group of the patient, in order to be able to identify potential safety signals specific to a particular population

I. Product Complaints

A Product Complaint is defined as any written or oral information received from a complainant that alleges deficiencies related to identity, quality, safety, strength, purity, reliability, durability, effectiveness, or performance of a product after it has been released and distributed to the commercial market or clinical trial.

J. Exchange of Single Case Reports with Genentech

[name] will be responsible for collecting all protocol-defined Adverse Events (AEs)/Serious Adverse Events (SAEs) (related and not related to the product), pregnancy reports, other Special Situation reports, Non-Serious AESIs, Product Complaints (with or without an AE) where the patient has been exposed to the Product.

It is understood and agreed that [name] will perform adequate due diligence with regard to obtaining follow-up information on incomplete case safety reports.

In addition, reasonable attempts must be made to obtain and submit the age or age group of the patient in order to be able to identify potential safety signals specific to a particular population.

[name] agrees to allow requests for follow-up information from Genentech, for instance, in order to fulfill regulatory obligations, or where the requested information is not already routinely covered by standard follow-up activities (e.g. clarification of data discrepancies, or to request typical confirmatory laboratory data or batch numbers for biologics and other advanced therapies). Genentech will not contact the reporter directly for such data, but will route all such requests for follow-up to the provided [name] contact.

Transmission of these reports (initial and follow-up) will be either electronically via email or by fax to the following email address/fax number:

[contact]

Email: [contact]

Product Complaints without an AE

All Product Complaints without an AE should be reported via:

PC [contact] (M-F: 5 am to 5 pm PST)

The completed MedWatch form should be sent to the Genentech contact specified above to report applicable events.

Regardless of the method used, the Batch ID/lot ID for biologics associated with AE/Special Situation/Scenario/PC/AESI must be included.

Reporting Timeline for Applicable Events

Transmission of the applicable event reports (initial and follow-up) will be sent within the timelines specified below:

Type of Report	Timelines
Serious Adverse Events (related and not related to the Product)	
Special Situation Reports (With or without AE and pregnancy)	30 calendar days from awareness date
Product Complaints (With or without AE)	
AESI	

K. Case Transmission Verification of Single Case Reports

The Parties will verify that all Single Case Report(s) have been adequately received by Genentech, via the exchange of a quarterly Line Listing that includes all fields detailed in Appendix 2: Content Required in the CTV Line Listing, documenting Single Case Report(s) sent by [name] to Genentech in the preceding quarter. The quarterly Line Listing will be exchanged within seven (7) Calendar days of the end of the agreed period. Following CTV, Single Case Report(s) which have not been received by Genentech shall be forwarded by [name] to Genentech within five (5) Calendar days from the request.

At the end of the study, a final cumulative Case Transmission Verification report will be sent to Genentech.

Quarterly line-listings and cumulative/final CTV should be sent to [contact].

L. MedWatch 3500a Reporting Guidelines

In addition to completing appropriate patient demographic (Section A) and suspect medication information (Section C & D), the report should include the following information within the Event Description (Section B.5) of the MedWatch 3500A form:

Protocol number and title description

Description of event, severity, treatment, and outcome if known

Supportive laboratory results and diagnostics (Section B.6)

Investigator's assessment of the relationship of the adverse event to each investigational product and suspect medication

Follow-Up Information

- Additional information may be added to a previously submitted report by any of the following methods:
 - Adding to the original MedWatch 3500A report and submitting it as follow-up
 - Adding supplemental summary information and submitting it as follow-up with the original MedWatch 3500A form
 - Summarizing new information and faxing it with a cover letter including patient identifiers (i.e. D.O.B. initial, patient number), protocol description and number, if assigned, brief adverse event description, and notation that additional or follow-up information is being submitted (The patient identifiers are important so that the new information is added to the correct initial report)

MedWatch 3500A (Mandatory Reporting) form is available at
<https://www.fda.gov/media/69876/download>

M. Reporting to Regulatory Authorities, Ethics Committees and Investigators

Genentech, as the Marketing Authorization Holder, will be responsible for the reporting of individual case safety reports from the study to the regulatory authority in compliance with applicable regulations.

[name] will be responsible for the distribution of safety information to its own investigators, where relevant, in accordance with local regulations.

[name] will be responsible for the expedited reporting of safety reports originating from the Study to the Independent Ethics Committees/ Institutional Review Boards (IEC/IRB), where applicable.

N. Reporting Requirements for Adverse Events Originating from Patient Reported Outcomes (PRO)

Although sites are not expected to review the PRO data, if physician/study personnel become aware of a potential adverse event during site review of the PRO questionnaire data, he/she will determine whether the criteria for an adverse event have been met and, if so, these must be reported using the Adverse Event and Special Situation Reporting Form or MedWatch form.

O. Aggregate Reports and Safety Information

[name] will be responsible for the distribution of safety information to Site IRB:

[name]
[name]
[name]
[contact]

email: [contact]

For questions related to safety reporting, please contact Genentech Patient Safety:

[contact]

[contact] or [contact]

All summary reports submitted by the Sponsor-investigator to any health authority should also be sent to Genentech. Copies of such reports, as described below, should be emailed to Genentech at: [contact]

[name] will forward a copy of the Final Study Report to Genentech upon completion of the Study.

Study Close-Out

Any study report submitted to the FDA by the Sponsor-Investigator should be copied to Genentech. This includes all IND annual reports and the Clinical Study Report (final study report). Additionally, any literature articles that are a result of the study should be sent to Genentech. Copies of such reports should be mailed to the assigned Clinical Operations contact for the study:

[contact]

And to Genentech Patient Safety CTV oversight mailbox at: [contact].

Queries

Queries related to the Study will be answered by [name]. However, responses to all safety queries from regulatory authorities, Ethics Committees and Institutional Review Board or for publications will be discussed and coordinated between the Parties. The Parties agree that Genentech shall have the final say and control over safety queries relating to the Product.

[name] agrees that it shall not answer such queries from regulatory authorities and other sources relating to the Product independently but shall redirect such queries to Genentech.

Both Parties will use all reasonable effort to ensure that deadlines for responses to urgent requests from Regulatory Authorities and/or IRB/IEC for information or review of data are met. The Parties will clearly indicate on the request the reason for urgency and the date by which a response is required.

Signal Management and Risk Management

Genentech is responsible for safety signal management (signal detection and/or evaluation) for their own Product. However, it is agreed that [name], as Sponsor of the Study, will be primarily responsible for assessment of the benefit-risk balance of the Study.

If [name] issues safety communication relevant for Genentech (i.e., a safety issue that notably impacts on the benefit-risk balance of the Study and / or triggers any changes to the Study) this will be sent to Genentech within five (5) business days of its internal approval.

As needed, Genentech will reasonably assist [name] with signal and risk management activities related to the Product within the Study.

Genentech will also provide [name] with any new relevant information that may modify or supplement known data regarding the Product (e.g., relevant Dear Investigator Letter).

Compliance With Pharmacovigilance Agreement / Audit

The Parties shall follow their own procedures for adherence to single case reporting timelines. Each Party shall monitor and, as applicable, request feedback from the other Party regarding single case report timeliness in accordance with its own procedures. The Parties agree to provide written responses in a timely manner to inquiries from the other Party regarding single case reports received outside the agreed upon Agreement timelines. If there is any detection of trends of increasing or persistent non-compliance to transmission timelines stipulated in this Agreement, both Parties agree to conduct ad hoc or institute a regular joint meeting to address the issue. In case of concerns related to non-compliance of processes, other than exchange timelines, with this Agreement, the Parties will jointly discuss and collaborate on clarifying and resolving the issues causing non-compliance. Every effort will be made by the non-compliant Party to solve the non-compliance issues and inform the other Party of the corrective and preventative actions taken.

Upon justified request, given sufficient notice of no less than sixty (60) calendar days, an audit under the provisions of this Agreement can be requested by either Party. The Parties will then discuss and agree in good faith upon the audit scope, agenda and execution of the audit. The requesting Party will bear the cost of the audit.

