- (2) Enroll a single-arm, open-label trial of **40** Ocrelizumab-treated MS patients who are soon starting GLP-1 agonists, monitored prospectively for 2 years to measure MS **progression** (clinical disability worsening, stability or improvement) every 3 months, including (a) clinical assessments (e.g. EDSS, 25-foot timed walk, SDMT) as used in the ORATORIO trial of Ocrelizumab, (b) PROMs on progression in MS including fatigue, ambulation distance, mood; and (3) simple objective biomarkers of disease (e.g. plasma neurofilament light chain, glial fibrillary acidic protein).

Overview: Aims 1 and 2 will recruit participants simultaneously but draw upon MS participants at different points in their GLP-1 agonist treatment. Participants can enroll in either the cohort of Aim 1 (in-person or remote) or the open label trial of Aim 2 (in-person only), not both aims. All participants will be Ocrelizumab-treated for MS upon study enrollment.

Study Endpoints

The primary outcome measure is **PIRA** (progression independent of relapse activity), based primarily on clinical assessment, dichotomized as present or not.¹²

For Aim 1, the cohort, patient-derived disability status (PDDS) score, and ambulation score (self-reported) will be the primary endpoints of interest.

For Aim 2, the clinical trial, PIRA will be measured pre-GLP-1 start and at study end (week 72). A composite score of disability, similar to the ORATORIO¹³ trial will be constructed including EDSS score, 25-foot timed walk, 9-hole peg test, and SDMT score.

Study Interventions/ Investigational Agent

Glucagon-like peptide-1 agonist agent is the study agent of interest. This study will not supply the GLP-1 drug but depend on the patient's clinical prescription of this drug. Similarly, all participants will be treated with Ocrelizumab for the indication of MS; however, the study will not provide Ocrelizumab as it will be part of the participant's routine clinical care.

Study Procedures

Inclusion Criteria, Aims 1 and 2:

- 1) Diagnosis of MS (2019 revised McDonald criteria) of any type (PPMS, RRMS, SPMS) by a neurologist,
- 2) Adult age 18-70 years,
- 3) BMI $\geq 24.0 \text{ kg/m}^2$,
- 4) Taken at least one dose of Ocrelizumab prior to study entry,
- 5) EDSS < 7.0 ,
- 6) Able to provide individual informed consent,
- 7) MRI available to confirm the diagnosis of MS.

Exclusion Criteria, Aims 1 and 2:

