***Additional Inclusion Criteria Aim 2:**

- 8) Able to present for baseline and follow up in person,
- 9) Unexposed to a GLP-1 agonist in the past year,
- 10) Starting on a GLP-1 agonist in the next <6 months,
- 11) Plan to be exposed to GLP-1 agonist for a minimum of 72 weeks following enrollment.

Participant Population(s)

Accrual Number:	Category/Group:	Consented/Enrolled:
Local	Individuals with MS already treated with Ocrelizumab and GLP-1 agonist	60
	Ocrelizumab-treated MS patients initiating GLP-1 agonist	40
Study-wide		
Total:		100

RECRUITMENT METHODS:

Potential participants will be identified through online research advertising webpages (e.g., ClinicalTrials.gov, Northwestern's clinical trials website), the investigator's connections with MS neurologists in the practice and surrounding practices, advertisements in MS clinics, the National MS Society local chapter's and national websites, MS physician networks, social media directly to patients, flyers in the medical infusion center, weight loss and nutrition clinics in the region, and through clinic newsletters and the word of mouth.

Interested patients will be screened through an online RedCap™ form for the study's eligibility criteria. Medical records review will occur by the investigators to ensure the criteria are met. Participants will then be called by telephone or met in person to describe the study procedures in detail.

CONSENT PROCEDURES:

Consent will be taken by a trained study team research coordinator or physician. All consent will be written on a standardized consent form, in English. Consent may be performed electronically using REDCap e-sign with an institutionally approved account. Participants will be given >24 hours to review the consent form and provide consent. Given the complexity of the study tasks including multiple self-reported variables, only participants who are able to provide their own consent will be enrolled.

Vulnerable Populations

Vulnerable populations will not be enrolled. Participants who lack capacity to voluntarily consent (e.g. institutionalized, dementia) are excluded as per the criteria listed above.

STUDY PROCEDURES:

Aim 1 will allow fully remote participation, drawing from geographically diverse settings throughout the USA. Participants in Aim 1 do not need to visit the study site in person or be

independently mobile but must be continuously available during the study timeframe remotely for PROMs and study surveys and calls.

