Waist, Hip, Limb Circumferences		X	X	X	X	X
Skin Fold Thickness		X	X	X	X	X
Neurological Examination	X	X	X	X	X	X
EDSS & Ambulation Score		X	X	X	X	X
Vital Signs (ht, wt, BMI, blood pressure, heart rate, respiratory rate)	X	X	X	X	X	X
PDDS		X	X	X	X	X
PROMS		X	X	X	X	X
QOL54-MS		X	X	X	X	X
Medication Adherence Questionnaire (GLP-1-focused)		X	X	X	X	X
25-foot timed walk test		X	X	X	X	X
Food Frequency Questionnaire		X	X	X	X	X
Physical Activity Questionnaire		X	X	X	X	X
9-Hole Peg Test		X	X	X	X	X
SDMT+PASAT		X	X	X	X	X
Blood Draw: CBC/differential +Chemistry	X					X
NFL-2, plasma		X	X	X	X	X
GFAP, blood		X	X	X	X	X
Vitamin D		X				X
Beta-HCG (urine) (invoiceable)	(X)	(X)	(X)	(X)	(X)	(X)
MRI Brain, 1.5T (not billed to study)	X	X			X	X

Allocation and Blinding

All participants will be treated with the two drugs of interest: Ocrelizumab and the GLP-1 agonist. The participants will be blinded to the study outcome of interest, i.e. progression or PIRA. The investigators will not be blinded to the study outcome. The participants will not have access to their prior PDDS scores on file, earlier in the study. The EDSS raters will not have access to the prior EDSS scores on file, earlier in the study. The statisticians will not be blinded to the study outcome.

Criteria for Study Drug Discontinuation in a Single Participant

Reasons for GLP-1 agonist drug discontinuation will be at the discretion of the treating prescriber include: (1) laboratory test abnormalities (e.g. transaminitis) whether related to the drugs or not; (2) intercurrent illness; (3) severe intolerance to the GLP-1 agonist; (4) lack of access to the GLP-1 drug within an affordable range; (5) patient preference; (6) achieved weight target earlier than anticipated; or (7) any other reason as determined by the prescribing physician or study principal investigator.

Criteria for Study Withdrawal of a Participant

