Participants who discontinue GLP-1 agonist drugs for any reason, including tolerability, cost, desired weight loss outcome, etc., will continue to be observed until the end of the study period. It is possible that participants will have periods of discontinuation and then resume GLP-1 agonist treatment. The participant will be observed until (a) week 72 visit (i.e. end of study period), (b) participant withdrawal with no consent to continue monitoring, or (c) investigator-decided withdrawal of a participant from the study (e.g. severe medical illness preventing study completion, departure far from study site, etc.).

Participant Compensation for Involvement in Research Procedures

Aim 1: Each participant will receive 75 USD every 3 months with a total of up to **600 USD**.

Aim 2: Each participant will receive 150 USD at baseline and 100 USD every subsequent visit occasions and then 150 USD at the final study visit with a total of up to **500 USD**.

Participants will have the option to receive cash or a gift card. Participants who receive cash will need to provide their social security number for the reporting of taxable income to the Internal Revenue Service, according to applicable laws.

There is no anticipated drug development or future product anticipated in this study. A study participant will not have any right to compensation or ownership interest related to such development.

RISKS AND BENEFITS:

Risks to Participants

Participants in this study may have side effects of the medications under investigation including both Ocrelizumab and the GLP-1 medication, although these will be given in the context of clinical care for U.S. Food and Drug Administration (FDA)-approved indications. In particular, the GLP-1 class of medications is known to cause gastrointestinal symptoms, including nausea, vomiting, early satiety, and abdominal discomfort. These are considered reversible, common (approximately 1/3 of all people treated with a GLP-1 medication), and expected. These risks are often mild to moderate and in some cases may lead to early discontinuation of the medication if poorly tolerated. Participants may experience injection-site reactions which could be bothersome.

An additional risk is that participants will be psychologically burdened by repeated testing and surveying throughout the study; however, no clinical harm is anticipated from surveys or the clinical assessments done during the study procedures.

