Variables of interest will be reported using descriptive frequency-based statistics (e.g. mean, median, range). Subgroups of interest (e.g. by gender, disability level below or above the median, etc.) will be compared using t-tests and tests of two proportions as appropriate. Repeated measures (e.g. weight) will be graphed and displayed. Change in values will be reported (final minus starting weight). If needed to report an outcome, repeated measures analyses, will be made using generalized linear models. Incidence of tolerability issues will be reported as the number of events per number of person-months of observation available.

Aim 2:

This will be an intention to treat analysis. All participants who enroll in the single-arm study will be analyzed to the end of their study participation, either the end of the planned study period or time of withdrawal. Data will be analyzed in aggregate with descriptive subgroup analyses performed with the following variables and subgroupings of interest: (1) sex at birth, (2) age at enrollment below or above the median age, (3) duration of GLP-1 (72 weeks versus early discontinuation), (4) BMI group (<30.0 kg/m², 30-39.9 kg/m², >40.0 kg/m², and (5) EDSS score at enrollment above or below the median.

The primary outcome measure is PIRA, dichotomized as present or not, as measured by the rater-determined composite functional outcomes score. This includes the EDSS score with contributions by the 9-hole peg test, SDMT, and 25-foot walking test, and will be constructed as presented in the ORATORIO trial for Ocrelizumab in primary progressive MS vs. placebo.

EDSS will be measured pre-GLP-1 (enrollment) and at the participant's end of study (i.e. one of (a) the end of planned study enrollment period, (b) administrative withdrawal, or (c) participant withdrawal). A positive change in EDSS score of 1.0 points with a baseline EDSS of <5.0 or a positive change in EDSS score of 0.5 points or more with a baseline EDSS score of 5.0 or higher will be considered PIRA. EDSS will be captured at each study visit but the first and last EDSS scores will contribute to the assessment of PIRA for the primary study outcome's hypothesis testing. The use of the EDSS scores at each q24week study visit will also be used in a generalized linear model to determine disability level worsening at any timepoint.

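### Aim 2 ties neither the reference EDSS nor the week 24/48/72 visits to the first GLP-1 dose, so persisting worsening before that dose can count as PIRA

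*Protocol*

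**What the plan says.** All of this is in the Protocol.

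- **Start of drug.** Additional Inclusion Criteria Aim 2, criterion 10: "Starting on a GLP-1 agonist in the next <6 months". No origin for the window is given. Criterion 11 asks for a plan of at least 72 weeks' exposure, counted from enrolment.
- **Control of the start date.** Study Interventions/ Investigational Agent: "This study will not supply the GLP-1 drug but depend on the" participant's own prescription.
- **Reference and final EDSS.** The Aim 2 analysis text (under Data Management and Confidentiality) says "EDSS will be measured pre-GLP-1 (enrollment) and at the" end of the participant's study, and that "the first and last EDSS scores will contribute to the assessment of PIRA" for the primary hypothesis test. The endpoint section gives no maximum interval to the first dose (Study Endpoints: "PIRA will be measured pre-GLP-1 start and at study end (week 72").
- **End of observation.** It is a study week, not a time since first dose (Criteria for Study Withdrawal of a Participant: "The participant will be observed until (a) week 72 visit (i.e. end of study period").
- **Schedule.** Table 2 lists "EDSS & Ambulation Score" at Baseline, weeks 24, 48 and 72, and unscheduled visits. Screening and Baseline are separate columns with no stated interval, and no visit is triggered by the first dose.
- **Analysis set.** "All participants who enroll in the single-arm study will be analyzed to the end of their study participation", so late starters and non-starters are included.
- **Comparator.** The sample size justification sets the PIRA proportion against a known proportion and states that there is no comparison group.

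**The concern.** Aim 2 needs a time zero at which exposure begins. The protocol names enrolment instead, while letting exposure begin months later on a date the study does not set. A first-versus-last EDSS comparison cannot tell worsening before the first dose from worsening after it. If the worsening arises while the participant is waiting and is still there at the last EDSS, it is recorded as PIRA on the combination. Transient worsening would not count.

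The protocol hopes to learn whether GLP-1 agonists protect against PIRA (Potential Benefits to Participants). Unexposed time moves the observed proportion toward what this population would show without the drug, whether the drug helps or harms. In a randomised trial a control arm would carry the same lead-in. Here none does, and enrolling more participants would not shrink the effect.

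**Working it through.** The plan gives no figure for the start delay or its effect, so there is none to reproduce. The sizes below are illustrations. Whether 40 participants can detect 10 points is a separate question, and nothing here rests on it.

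**Inputs from the protocol:** start within just under 6 months, taken as 26 weeks; follow-up 72 weeks; n = 40 in Aim 2; PIRA up to 24% in relapsing MS, with no time horizon; a difference of 10 points.

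**Assumptions:** 24% is this population's own off-drug risk over 72 weeks; hazards are constant; the drug acts at once; all participants share the same delay d; worsening persists to the last EDSS.

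**Step 1, unexposed share.** At the limit, 26/72 = 36.1% for one participant, leaving 72 − 26 = 46 weeks of possible exposure by week 72.

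**Step 2, observed risk.** Off-drug weekly hazard h0 = −ln(0.76)/72. On-drug hazard h1 = −ln(0.86)/72 for a fall to 14%, or −ln(0.66)/72 for a rise to 34%. Observed risk = 1 − exp{−[d·h0 + (72 − d)·h1]}.

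| Delay d (weeks) | Observed risk, true 14% | Difference from 24% | Observed risk, true 34% | Difference from 24% |
|---|---|---|---|---|
| 0 | 14.0% | 10.0 | 34.0% | 10.0 |
| 4 | 14.59% | 9.41 | 33.48% | 9.48 |
| 8 | 15.17% | 8.83 | 32.96% | 8.96 |
| 13 | 15.90% | 8.10 | 32.30% | 8.30 |
| 26 | 17.75% | 6.25 | 30.55% | 6.55 |

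**Step 3, pre-dose events.** The chance of worsening before the first dose is 1 − exp(−d·h0). At d = 13 this is 4.83%, or 1.93 of 40; if only half persist, about 0.97. With a 10% background over 72 weeks it is 1.88%, or 0.75 of 40; about 0.38 if half persist.

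**Step 4, scale.** The standard error at n = 40 is √(0.24 × 0.76/40) = 6.75 points. The loss at 13 weeks, 10.0 − 8.1 = 1.9 points, is 1.9/6.75 = 0.28 of it.

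**Step 5, cost of moving Baseline.** With a proportion w withdrawing over 72 weeks (10–20% assumed), the number lost while waiting d weeks is 40 × [1 − (1 − w)^(d/72)]. For w = 10% this is 0.75 at 13 weeks and 1.49 at 26. For w = 20% it is 1.58 and 3.10.

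**Step 6, calendar.** Enrolment in December 2026, with a 26-week wait and 72 weeks of follow-up (98 weeks), ends between 17 October and 16 November 2028. To keep last participant out within April 2028, the last Baseline visits must fall by 14 November to 13 December 2026 (1 and 30 April 2028 less 72 weeks).

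**The case against.** **The harmful reading is one of several.** The Aim 2 description says participants are soon to start, and the analysis text treats pre-GLP-1 and enrolment as one time point. Criterion 11 counts exposure from enrolment. Eligibility is screened on an online form, so the window may run from screening. A GLP-1-focused adherence questionnaire at Baseline hints that Baseline is near the first dose. This stands: a reader might infer that the protocol builds in a 26-week lead-in, and it does not. It leaves the anchor open. But none of these hints fixes a date, and the analysis text's own gloss is enrolment.

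**A reader might also infer that criteria 10 and 11 contradict each other.** They do not. Criterion 11 asks only for a plan. It shares the loose anchor.

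**The damage can partly be assessed afterwards.** EDSS is also taken at week 24, and medication is reviewed at every visit. If the window runs from Baseline, everyone who starts as planned has started by about week 26. Worsening first seen at week 48 or 72 is then post-dose, apart from roughly weeks 24–26 in the latest starters. This stands, so it would be too strong to say that nothing can be done later. The check bounds the contamination. It cannot separate pre-dose from post-dose worsening seen at week 24 in someone who started mid-window.

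**The sizes rest on stacked assumptions.** This stands. Aim 2 admits every MS type, and 24% is an upper figure for relapsing MS. If this population's own rate is lower, unexposed time pulls toward that lower rate, so a shrinking gap from 24% is not established in general.

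**Baseline timing could be left to an analysis plan.** It cannot be settled there alone: an analysis plan cannot supply an EDSS at first dose if no visit was scheduled then.

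**Conclusion.** The point holds as an unfixed time zero, and it should be corrected before participants enrol. Followed as written, with Baseline at enrolment, the plan can count persisting worsening from up to just under 26 unexposed weeks out of 72 as PIRA, with no concurrent group to offset it.

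The likely size is modest. Under the stated assumptions the loss from a true 10-point reduction is 0.6 to 1.9 points at delays of 4 to 13 weeks, small beside a standard error of about 6.8 points. It reaches 3.75 points only if everyone starts at the limit. The protocol gives no distribution of delays, so none of these is a forecast. The case for acting is that the pull is systematic, and that a reference EDSS near the first dose cannot be recovered once the visit has been missed.

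**What to change.** **Change**

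1. In the Aim 2 analysis text and Table 2, schedule the existing Baseline visit, with the reference EDSS, shortly before the first GLP-1 dose. Count weeks 24, 48 and 72 from that dose. The visits follow the prescription, which stays with the prescriber.
2. State what date the window in criterion 10 runs from, and align criterion 11 with the same anchor.
3. Record the first-dose date for every participant.
4. Keep the all-enrolled analysis. For anyone not started when the window ends, do Baseline then and report these participants separately, because their time zero differs.
5. As a supporting analysis, report PIRA by whether worsening was already present at week 24 and by first-dose date. If the visits are not re-anchored, this is the minimum, and it bounds the problem without removing it.

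**Cost**

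This needs a protocol amendment but no added visit. Late starters finish later: at the limit, in October–November 2028, past the planned summer 2028 closure, unless consent is timed near the expected start. About 0.8 to 3.1 of 40 could withdraw while waiting, under the assumed 10–20% withdrawal, and would have no reference EDSS. Scoring an EDSS from the neurological examination already listed at Screening would give them a fallback.

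Re-checking eligibility at a later Baseline, and reconciling the Aim 2 description of 2 years with 3-monthly assessment against the 72-week, 24-weekly schedule, are separate matters and not part of this change.
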